5.4 Trial entry and randomisation procedure

Prior to recruitment of patients into the trial, the Principal Investigator for each site, or their designee, should have returned all required documentation to the STOMP Trial Office, and the site personnel involved with the STOMP trial must have received appropriate training.

Patient eligibility will be established before treatment randomisation and randomisation codes will be assigned strictly sequentially as patients become eligible for randomisation, with eligible patients being randomised in a 2:1:2:1 ratio according to the following pattern:

	300 mg BD	200 mg TDS	Total
Olaparib	33.3 % (2)	33.3 % (2)	66.6 %
Placebo	16.6 % (1)	16.6 % (1)	33.3 %

STOMP Protocol

Randomisation will be stratified by disease extent (M0 vs M1a/b with any T or N stage, please see Appendix 1 for the AJCC TNM staging for lung cancer) and prior radiotherapy (concurrent vs sequential vs none). The actual treatment given to individual patients will be determined by a randomisation scheme that has been loaded into the Cenduit Interactive Web Recognition System (IWRS) database which is, for the purposes of randomisation, accessed by Cancer Research UK Clinical Trials Unit (CRCTU) on behalf of randomising sites.

Randomisation Office: [name] (9 am till 5 pm Monday to Friday excluding University of Birmingham closed days)

A blockrandomisation will be generated and all sites will use the same list in order to minimise any imbalance in the number of patients assigned to each treatment group.

For all subsequent visits the web IWRS system should be used by the site research team to record visits and dispense the required medication.

The following information will be required at randomisation;

- Name of hospital, Investigator and person randomising the patient
- Confirmation that the patient is eligible for the trial
- Confirmation that the patient has given written informed consent
- An anonymised copy of the screening CT scan report (fax to [name] immediately prior to randomisation) to demonstrate response to prior treatment. The following should be clearly stated on the report: FAO: STOMP trial office, site name, patient's initials and date of birth.
- Confirmation of extent of disease and whether or not the patient has had any prior radiotherapy

Patients will be identified to Cenduit using the site number, trial number and date of birth. Once a patient has been randomised, e-mail confirmation will be sent to the sites nominated contact(s) and the STOMP Trial Office. The original patient's Informed Consent Form must be retained in the ISF for inspection, and a copy sent to the STOMP Trial Office in the post. A copy of the Randomisation Form must also be filed in the ISF and the patients details (trial number, initials, and date of birth) entered onto the screening and enrolment log.

Cenduit will inform the sites nominated contact(s) of the MedID number to be allocated to the patient at the randomisation visit. A member of the research team (to be decided by the hospital) will log in to the Cenduit IWRS for each subsequent dispensing visit for assignment of a new MedID number. The MedID number dispensed at each visit will correspond to the treatment to which the patient was originally randomised or will assign a dose-reduced treatment where relevant.

It is recommended that patients commence trial treatment as soon as possible after randomisation, and ideally within 3 calendar days. Delays in initiation of treatment longer than this will need to be documented and approved by the STOMP Trial Office.

If a patient discontinues participation in the trial, then their trial number cannot be re-used.

6.0 TREATMENT DETAILS

6.1 Treatment schedule

All STOMP treatments will be given in an outpatient setting and according to the schedule stated below. Treatment must start within the time limits defined in the eligibility criteria – no more than 42 days after day 1 of the last chemotherapy cycle, or 21 days after the last radiotherapy fraction (whether thoracic or cranial). For patients who receive chemotherapy followed by radiotherapy, the radiotherapy must begin within 35 days from the start of the last chemotherapy cycle. Where concurrent treatment is given, and radiotherapy and chemotherapy finish on the same day, the chemotherapy timeline should be followed.

Treatment with olaparib/placebo 300mg po bd or 200mg tds, continuously will be given until death, disease progression, unacceptable toxicities or withdrawal of patient consent up to a maximum of 2 years.

The tablets should be taken at the same times each day, with a glass of water. Tablets can be taken with a light snack but should not be taken with a heavy meal because of the potential effect of food on absorption. The tablets should be swallowed whole and not chewed, crushed, dissolved or divided.

If vomiting occurs shortly after the tablets are swallowed, the dose should only be replaced if all of the tablets can be seen intact and counted. Should any patient enrolled on the trial miss a scheduled dose for whatever reason (e.g., as a result of forgetting to take the tablets or vomiting), the patient will be allowed to take the scheduled dose up to a maximum of 2 hours after that scheduled dose time. If greater than 2 hours after the scheduled dose time, the missed dose is not to be taken and the patient should take their allotted dose at the next scheduled time.

Patients will continue with trial drug until objective disease progression occurs (determined by RECIST 1.1 – see Appendix 3), as long as in the Investigator's opinion they are benefiting from treatment and they do not meet any other discontinuation criteria.

Patients will remain blinded to the trial team until after the final analysis. No crossover to olaparib is permitted.

6.2 Dose modification

Any toxicity observed during the course of the trial can be managed by dose interruption or dose reduction if deemed appropriate by the Investigator. Once the dose of trial drug has been reduced, under no account should it be re-escalated. All dose reductions and interruptions (including any missed doses), and the reasons for these will be recorded on the Case Report Form (CRF) and in the Patient Diary.

For CTCAE (version 4) grade 1 or 2 AE which the Investigator considers to be related to administration of trial drug, interruptions are discretionary.

For CTCAE **grade 3 or 4 AEs** which the Investigator considers to be related to administration of trial drug, treatment must be interrupted. Such interruptions should continue until the patient recovers completely or the toxicity reverts to CTCAE grade 1 or less. If this is not achieved within a maximum of 4 weeks (28 days) and/or the patient has already undergone a maximum of 2 dose reductions (to the minimum dose), then the patient must permanently discontinue treatment with trial drug. If all toxicity is appropriately resolved within 4 weeks, then the patient should restart treatment with trial drug, but at the 1st dose reduction level according to Table 6.2. If an AE recurs at grade 3 or 4, treatment should be interrupted again (for a maximum of 28 days as detailed above) and, if it resolves within 4 weeks, a second dose reduction should be made. If, on re-starting treatment, the event

STOMP Protocol

continues to occur, the patient must permanently discontinue trial drug. Patients are only allowed two dose reductions.

Full haematology assessments for safety (including Hb, platelets, WBC, and ANC) should be performed at each visit and when clinically indicated. If the absolute value is not available please record percentage. Coagulation (activated partial thromboplastin time [APTT] and international normalised ratio [INR]) will be performed at baseline if clinically indicated unless the patient is receiving warfarin. Patients taking warfarin may participate in this trial; however, it is recommended that prothrombin time (INR and APTT) be monitored carefully at least once per week for the first month, then monthly if the INR is stable.

Management of leukopenia and/or anaemia:

An exception to the management of olaparib-related toxicity is the occurrence of leukopenia and/or anaemia. In this case, the AE should be managed as deemed appropriate by the Investigator (with growth factor e.g. G-CSF or blood transfusions). However, growth factors must be discontinued once the AE has recovered to CTCAE grade 1 or better. They may be resumed, if necessary, if leukopenia/anaemia develops again and discontinued once it recovers.

- Patients who develop a requirement for repeated blood transfusions within 4-6 weeks should be dose reduced
- Patients who develop grade 3 anaemia should be dose reduced

Management of prolonged haematological toxicities including anaemia, neutropenia or thrombocytopenia whilst on trial treatment:

If trial treatment is interrupted/delayed because of one or more of the following:

- ≥ 2 week interruption/delay in trial treatment due to CTCAE grade >2 neutropenia
- ≥ 2 week interruption/delay in trial treatment due to CTCAE grade >2 thrombocytopenia
- ≥ 2 week interruption/delay in trial treatment due to CTCAE grade >2 anaemia and or development of blood transfusion dependence

Weekly blood counts should be performed during the trial treatment interruption/delay. If the levels have still not recovered to CTCAE grade ≤ 1 after 4 weeks of dose interruption, the patient should be referred to a haematologist for further investigations. Bone marrow analysis or blood cytogenetic analysis should be considered at this stage according to standard haematological practice. Development of MDS/AML should be reported as a Serious Adverse Event (SAE) and full reports must be provided by the Investigator for documentation on the pharmacovigilance database.

Pulmonary symptoms

If new or worsening pulmonary symptoms (e.g. dyspnoea) or radiological abnormality occurs, an interruption in trial drug dosing is recommended and a diagnostic workup (including a high resolution CT scan) should be performed, to exclude pneumonitis. Following investigation, if no evidence of abnormality is observed on CT imaging and symptoms resolve, then trial treatment can be restarted, if deemed appropriate by the Investigator. If significant pulmonary abnormalities are identified, these need to be discussed with the Chief Investigator.

Table 6.2 Dose reductions for olaparib / placebo

Reduction	Dose Level	
Initial Dose Level	300mg bd	200mg tds
1 st dose reduction	250mg bd	150mg tds
2 nd dose reduction	200mg bd	100mg tds
3 rd dose reduction	No further reduction allowed withdraw patient	No further reduction allowed - withdraw patient

Surgery and radiotherapy

Trial drug should be stopped before surgery and re-started following recovery. No stoppage of trial drug is required for any biopsy procedures.

Trial drug should be discontinued for a minimum of 7 days before a patient undergoes therapeutic radiation treatment. Dose interruption is not required for single palliative fractions.

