7.4.2 Withdrawal from Treatment

If a patient chooses to withdraw from treatment only, the patient should discontinue treatment but continue to be assessed in accordance with the protocol (including continuation of CT scans).

If a patient wishes to withdraw from the trial (i.e. including trial specific assessments), but is willing for further data to be supplied to the STOMP Trial Office, then further routine “follow-up” data (e.g. progression status, survival, further treatment) will continue to be supplied by the Investigator to the STOMP Trial Office.

Patients may be discontinued from Investigational Medicinal Product (IMP) in the following situations:

- Patient decision. The patient is at any time free to discontinue trial drug, without prejudice to further treatment
- After suffering an AE
- Severe non-compliance to trial protocol
- Any CTCAE grade 3 or 4 events that have not reverted to CTCAE grade 1 or less within 4 weeks (28 days). At the Investigator’s discretion, following dose interruption, patients may be considered for dose reductions providing they have not already undergone the maximum number of dose reductions allowed - for guidelines see Section 6.2. However, if upon re-challenging with olaparib/placebo at the lowest reduced dose any CTCAE grade 3 or 4 AE recur, the patient must be discontinued
- Objective progression according to RECIST 1.1

If the patient decides to withdraw from the trial and is not willing to supply any further data then this wish should be explicitly stated in the source data.

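### Section 6.4.5 waives drug interruption for palliative bone radiotherapy of any length, citing Section 6.2, which exempts only one-off fractions; Section 7.4.2 also leaves the 28-day toxicity stop ambiguous

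*Protocol*

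**What the plan says.** **Radiotherapy.** Section 6.2, in its paragraphs on surgery and radiotherapy, has trial drug stopped for at least 7 days ahead of therapeutic radiation, a term it does not define. It lifts the need to interrupt only for palliative fractions given singly. Section 6.4.5 allows palliative radiotherapy for pain from bone metastases known at baseline, provided the investigator does not see them as a sign of clinical progression. It then says that no interruption is needed and gives Section 6.2 as its reference. It does not mention the number of fractions.

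**Toxicity.** Section 6.2 covers grade 3 or 4 adverse events that the investigator attributes to trial drug. Dosing must be interrupted. If the event has not come down to grade 1 or less within 28 days, or both dose reductions have been used, "then the patient must permanently discontinue treatment with trial drug". The way back is conditional: "If all toxicity is appropriately resolved within 4 weeks, then the patient should restart treatment with trial drug", at a reduced dose. Leukopenia and anaemia are excepted and left to the investigator's management.

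Section 7.4.2 opens its list with "Patients may be discontinued from Investigational Medicinal Product (IMP) in the following situations". One item is "Any CTCAE grade 3 or 4 events that have not reverted to CTCAE grade 1 or less within 4 weeks (28 days". The same bullet then leaves a choice to the investigator: "following dose interruption, patients may be considered for dose reductions providing they have not already undergone the maximum number of dose reductions allowed", and it adds "for guidelines see Section 6.2". It then makes stopping compulsory in one case: if on re-challenge "at the lowest reduced dose any CTCAE grade 3 or 4 AE recur, the patient must be discontinued". Another item on the list is "Objective progression according to RECIST 1.1".

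**The concern.** Both looser passages cite Section 6.2, yet neither carries over the limit that Section 6.2 sets.

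For radiotherapy, an investigator who looks up palliative treatment goes to Section 6.4.5, finds a plain waiver, and has no reason to suspect that the section it cites is narrower. Section 1.2 of the Protocol says that loss of PARP 1 activity sensitises to radiation and that PARP inhibitors enhance its anti-tumour effect. The limit in Section 6.2 therefore plausibly has a safety purpose.

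For toxicity, an investigator who starts from Section 7.4.2 meets an unresolved event at 28 days, the word *may*, and an offer of dose reduction whose only stated condition is that reductions remain. The risk is a reduced-dose restart in a patient whose drug-related grade 3 or 4 event has not resolved. Dosing without any interruption is not at issue, because the bullet itself assumes that an interruption has taken place.

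At stake are patient safety and uniform handling of like patients across the sites of a multicentre trial.

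**Working it through.** No arithmetic applies. The check sets the rules side by side for the two situations in which they could diverge.

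| Situation | Section 6.2 | Section that cites it |
|---|---|---|
| One palliative fraction to a painful baseline bone metastasis | No interruption | 6.4.5: no interruption |
| Palliative course of more than one fraction, same indication | Outside the exemption; at least 7 days off drug if the course counts as therapeutic radiation | 6.4.5: no interruption |
| Drug-related grade 3 or 4 event, back to grade 1 or less within 28 days, reductions remaining | Restart at reduced dose | 7.4.2: dose reduction may be considered |
| Drug-related grade 3 or 4 event, not recovered at 28 days, reductions remaining | Permanent stop | 7.4.2: may be stopped; dose reduction may be considered; resolution condition not repeated |
| Grade 3 or 4 event not related to trial drug, not recovered at 28 days | This rule sets no compulsory stop | 7.4.2: may be stopped |

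**Row 2.** The divergence depends on whether a multi-fraction palliative course is therapeutic radiation. Section 6.2 does not say so directly. But if all palliative treatment already lay outside the 7-day rule, exempting single palliative fractions would serve no purpose. The natural reading is that longer palliative courses are covered. Section 6.4.5 then cites Section 6.2 for a wider exemption than Section 6.2 gives.

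**Row 4.** Three features of the text bear on how much the 7.4.2 bullet loosens the rule.

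- The verb *may* proves little. Objective progression is on the same list, and Section 7.2 makes stopping at progression compulsory.
- The bullet covers grade 3 or 4 events of any cause. For unrelated events (row 5), *may* is the right verb.
- The discretionary sentence refers to Section 6.2, and Section 6.1 continues drug only in patients who meet no other discontinuation criterion.

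These favour the stricter reading. What remains is that the dose-reduction offer sits in the bullet on events that have *not* resolved and names only one of the two conditions that Section 6.2 imposes.

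**Who is affected.** Row 2 concerns patients with painful bone metastases present at baseline who need more than one fraction and whose pain is not judged to be progression. Row 4 excludes leukopenia and anaemia. It includes thrombocytopenia, which Section 1.4 describes as occasionally reaching grade 3 or 4. For prolonged thrombocytopenia Section 6.2 adds weekly counts, and referral to a haematologist if it has not recovered after 4 weeks, but that paragraph does not itself say whether drug may be restarted.

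**The case against.** On radiotherapy, the defence is that Section 6.4.5 cites Section 6.2, so a reader who follows the reference reaches the single-fraction limit. It can add that Section 6.2 never states that multi-fraction palliative treatment is therapeutic radiation, so the suggested amendment relies on an inference, and that a 7-day wait before treating bone pain is a real cost to the patient. The inference and the cost are fairly stated and stand as qualifications. The cross-reference does not rescue the text: it presents Section 6.2 as authority for a waiver that Section 6.2 does not give, and a site has no cue to look for a limit. If the sponsor did intend the wider waiver, Section 6.2 would need amending instead; the two sections cannot both stand as written.

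On toxicity, the defence is stronger. A reader might infer that Section 7.4.2 flatly contradicts Section 6.2 and permits a restart with unresolved toxicity. The documents do not support that. Section 7.4.2 nowhere says that drug may be restarted before recovery. Its offer comes after an interruption, which under Section 6.2 ends for these events either in recovery or in permanent discontinuation. With the reference to Section 6.2, the compulsory stop at progression on the same list, and the wider scope of the bullet, the stricter reading is the better one. What survives is an omission that could mislead a site reading the bullet alone.

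**Conclusion.** The main point holds: Section 6.4.5 is wrong as written, because it waives interruption without a fraction limit on the authority of a section that exempts only single fractions. It rests on one assumption, that longer palliative courses fall under therapeutic radiation in Section 6.2; the wording of the exemption implies this but does not state it.

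The secondary point holds only as an ambiguity in Section 7.4.2, for drug-related grade 3 or 4 events other than leukopenia and anaemia that have not recovered at 28 days.

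The documents give nothing from which to estimate how often either case would arise, so no figure is offered. A reader might also infer harm to the primary comparison. The documents do not support that: Section 15.4 analyses all patients by intention to treat, and neither wording changes who is analysed, how progression is defined or the sample size. The effect is on patient safety and consistency between sites only, which is reason enough to correct the wording.

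**What to change.** - **Section 6.4.5:** replace the last sentence with one saying that interruption can be omitted for a single palliative fraction, and that for longer courses trial drug is interrupted as in Section 6.2.
- **Section 7.4.2:** state that a patient whose drug-related grade 3 or 4 event has not come down to grade 1 or less within 28 days must stop trial drug permanently, with leukopenia and anaemia managed as in Section 6.2. Add that, for these drug-related events, dose reduction is open only if the event has reverted within 28 days and reductions remain. Keep *may* for unrelated events, and keep the existing compulsory stop for recurrence at the lowest dose.

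The cost is an amendment to one sentence and one bullet, plus a note to sites. There is one small clinical downside: the 7-day interval can delay a multi-fraction course given for pain. It does not arise for a single fraction.

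### Section 6.2 gives a grade-based dose reduction for grade 3 anaemia but, read literally, none for grade 4

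*Protocol*

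**What the plan says.** Section 6.2 of the Protocol builds the dose rules in layers.

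- **Opening permission.** "Any toxicity observed during the course of the trial can be managed by dose interruption or dose reduction if deemed appropriate by the Investigator".
- **General rule.** For grade 3 or 4 events "which the Investigator considers to be related to administration of trial drug, treatment must be interrupted". If the event resolves within 4 weeks, the patient restarts at the first reduction level of Table 6.2. At most two reductions are allowed.
- **Exception.** "An exception to the management of olaparib-related toxicity is the occurrence of leukopenia and/or anaemia". No grade limit is attached. "In this case, the AE should be managed as deemed appropriate by the Investigator", with growth factor or transfusion given as examples.
- **Reductions added back under the exception.** There are two bullets: "Patients who develop a requirement for repeated blood transfusions within 4-6 weeks should be dose reduced" and "Patients who develop grade 3 anaemia should be dose reduced".
- **Prolonged haematological toxicity.** A separate block applies after an interruption or delay of at least 2 weeks, including one "due to CTCAE grade >2 anaemia and or development of blood transfusion dependence". It calls for weekly blood counts and, if there is no recovery after 4 weeks, referral to a haematologist.

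Elsewhere, Section 7.1.3 schedules haematology at the 4-weekly visits, and Section 6.2 adds counts when clinically indicated. Section 10.3.1.1 has sites record, for each sign or symptom, the highest grade since the previous visit.

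**The concern.** A toxicity rule should be at least as strict at the more severe grade. Here the exception removes anaemia from a rule that covers grades 3 and 4 together, and the bullet that restores a reduction names only grade 3. Read literally, a patient with grade 3 anaemia should step down a dose level, while for a patient with grade 4 anaemia the grade itself calls for no step.

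This concerns the organ where toxicity is expected: Section 1.4 names bone marrow as the target organ in the toxicology studies and lists anaemia first among the associated effects. Two sites could handle the same grade 4 event differently and both be within the text. For example, a patient with grade 4 anaemia could receive a single transfusion, recover and continue at full dose. One transfusion does not meet the repeated-transfusion trigger, and no other bullet names grade 4.

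**Working it through.** No figure in the plan needs reproducing. The check sets the rules side by side, followed by the dose arithmetic from Table 6.2.

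**1. What each part of Section 6.2 provides**

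| Rule in 6.2 | Grade 3 anaemia | Grade 4 anaemia |
|---|---|---|
| General rule (interrupt, restart one level lower) | displaced by the exception | displaced by the exception |
| Exception (investigator's judgement) | applies | applies |
| Repeated-transfusion bullet | applies if met | applies if met |
| Grade-based reduction bullet | **applies** | **not named** |
| Prolonged-toxicity block (grade above 2) | counts and referral | counts and referral |

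The two columns differ in one row only, and there the more severe grade has the weaker instruction.

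**2. Does the prolonged-toxicity block close the gap?** No. It covers both grades, but it starts only after at least 2 weeks of interruption or delay and leads to monitoring and referral, not to a reduction. It does show that the drafters knew how to write a threshold covering both grades, as does the general rule. This points to a slip in the bullet rather than an intended difference.

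**3. Can a patient be recorded at grade 4 without a recorded grade 3?** Yes. Scheduled haematology is 4-weekly and the form takes the highest grade since the last visit. Anaemia that passes through grade 3 between visits, or peaks at grade 4 within one interval, is entered as grade 4. Extra counts when clinically indicated make this less likely but do not exclude it.

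**4. Size of the dose step that depends on the wording** (Table 6.2)

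- Twice daily: 300 x 2 = 600 mg/day to 250 x 2 = 500 mg/day; -100/600 = -16.7%.
- Three times daily: 200 x 3 = 600 mg/day to 150 x 3 = 450 mg/day; -150/600 = -25%.

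These are differences in prescribed dose, not measures of harm.

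**5. How many patients?** Not derivable. The Protocol gives no rate of grade 3-4 anaemia, and Section 1.4 describes anaemia on olaparib as generally grade 1-2.

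**The case against.** The strongest reply is that the gap is almost entirely on paper. A patient who reaches grade 4 has ordinarily developed grade 3 on the way, so the bullet already applies. Most clinicians would read it as grade 3 or worse. Section 6.2 opens by allowing interruption or reduction for any toxicity, and the prolonged-toxicity block presupposes that drug is in fact interrupted for anaemia above grade 2. Repeated transfusions bring a reduction at any grade. The bullet says *should*, so even for grade 3 it is not an absolute requirement. All of this stands, and it is why the point is minor. It does not make the wording right: it relies on readers supplying a grade that the text leaves out, and step 3 of the check shows how a patient may be on record only at that grade.

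Two stronger readings are tempting, and the documents support neither.

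- *That the exception overrides the stop at the lowest dose.* A reader might infer this from "They may be resumed, if necessary, if leukopenia/anaemia develops again and discontinued once it recovers". That sentence is about growth factors, not trial drug. Section 7.4.2 makes discontinuation mandatory when any grade 3 or 4 event recurs at the lowest dose, with no carve-out for leukopenia or anaemia. Section 6.1 continues treatment only while no other discontinuation criterion is met. The stop already applies; at most a cross-reference is absent.
- *That grade 4 patients would accumulate a calculable excess dose over 4-6 weeks.* The repeated-transfusion bullet describes a window within which the need recurs, not a waiting time, so the trigger can be met early in it. Such a sum would also assume full dosing through grade 4 anaemia by an investigator who takes no action.

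**Conclusion.** The point holds as a minor wording error in an operative safety rule. By the letter of Section 6.2, grade 4 anaemia carries no grade-based dose reduction while grade 3 does. The conclusion rests on reading the exception as it is written, without a grade limit, and on the reduction bullet naming grade 3 alone. What is at stake per affected patient is the first reduction step shown above. Affected patients are those recorded only at grade 4, without repeated transfusions, whose investigator does not reduce the dose on judgement; they are likely to be few. Nothing here touches the PFS sample size, the significance level or the power, and there is no conflict with the discontinuation rule in Section 7.4.2.

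**What to change.** In the second reduction bullet under the leukopenia and anaemia exception in Section 6.2, insert *or 4* after *grade 3*, so that dose reduction applies to grade 3 or 4 anaemia. Section 7.4.2 and Table 6.2 need no change.

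The cost is two words in one bullet. The only downside is slightly less investigator discretion at grade 4, where the general rule for other toxicities already allows none.
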